##### **2.2.3 Safety endpoints**

- All-cause mortality
- Number of serious adverse events
- Number of hypoglycaemic events
- Number of genital infections
- Number of ketoacidotic events
- Changes in liver function parameters (AST, ALT, GGT)

**Ertugliflozin to Reduce Arrhythmic burden in ICD/CRT patientS (ERASE-Trial) – a phase III Study**

- Changes in renal function parameters (creatinine, eGFR)

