6.5 Adverse events of Special Interest (AESIs)

The term AESI relates to any specific AE that has been identified at the project level as being of particular concern for prospective safety monitoring and safety assessment within this trial, e.g. the potential for AEs based on knowledge from other compounds in the same class. AESIs need to be reported to the Pharmacovigilance Department of MSD within the same timeframe that applies to SAEs.

Patients with AESIs need to be followed up appropriately, regardless of the origin of the laboratory data (e.g. central, local etc.). The Investigator should consider which, if any, concomitant therapies should not be taken during evaluation. Discontinued treatments can be reintroduced per Investigator discretion.

The following are considered as AESIs:

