6.5.1 Hepatic injury

A hepatic injury is defined by the following alterations of hepatic laboratory parameters after randomisation:

- an elevation of AST and/or ALT ≥ 3 fold ULN combined with an elevation of total bilirubin ≥ 2 fold ULN measured in the same blood sample
- an isolated elevation of ALT and/or AST ≥ 5 fold ULN

These laboratory findings constitute a hepatic injury alert and the patients showing these abnormalities need to be followed up according to medical judgement.

In case of clinical symptoms of hepatic injury (icterus, unexplained encephalopathy, unexplained coagulopathy, right upper quadrant abdominal pain, etc.) without laboratory results (ALT, AST, total bilirubin) available, the Investigator should make sure these parameters are analysed, if necessary in an unscheduled blood test.

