6.5.2 Decreased renal function

Decreased renal function is defined by a creatinine value showing a ≥ 2 fold increase from baseline and is above the ULN.

For the AESI “decreased renal function” the Investigator shall collect an unscheduled laboratory sample for creatinine as soon as possible and initiate follow-up laboratory tests of creatinine according to medical judgement.

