6.5.4 Events involving lower limb amputation

This definition includes amputation (i.e. resection of a limb through a bone), disarticulation (i.e. resection of a limb through a joint) and auto-amputations (i.e. spontaneous separation of non-viable portion of the lower limb).

Not included in this definition are debridement (removal of callus or dead tissue), procedures on a stump (like stump revision, drainage of an abscess, wound revision etc.) and other procedures (e.g., nail resection or removal) without a concomitant resection of a limb (amputation or disarticulation).

Each lower limb amputation, disarticulation, or auto-amputation should be reported separately. The SAE report should include the date of the procedure, the level of amputation or disarticulation, the medical condition(s) leading to the procedure and if the patient had some of the known risk factor(s) for lower limb amputation.

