## 6 Summary of Study Data

All summary tables will be structured with columns for each treatment and overall in the order (overall, placebo, ertugliflozin) and will be annotated with the total population size relevant to that table, including any missing observations. All continuous variables will be summarized using the following descriptive statistics: n (non-missing sample size), mean, standard deviation. The frequency and percentages (based on the non-missing sample size) of observed levels will be reported for all categorical variables. Demographic and clinical characteristics to be summarized will include all relevant baseline variables.

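### Three of the four adverse events of special interest have no event-level safety endpoint: amputation is not listed, and hepatic and renal injury appear only as laboratory changes

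*SAP*

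**What the plan says.** Protocol 6.5 describes AESIs as "being of particular concern for prospective safety monitoring and safety assessment within this trial", so their purpose goes beyond expedited reporting to the manufacturer. It then lists four:

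- **Hepatic injury (6.5.1).** Either AST and/or ALT at least 3 times ULN "combined with an elevation of total bilirubin ≥ 2 fold ULN measured in the same blood sample", or ALT and/or AST at least 5 times ULN alone.
- **Decreased renal function (6.5.2).** Creatinine at least twice baseline and above ULN. When this occurs, "the Investigator shall collect an unscheduled laboratory sample for creatinine as soon as possible".
- **Metabolic acidosis, ketoacidosis and DKA (6.5.3).** Diagnostic criteria are tabulated for DKA.
- **Lower-limb amputation (6.5.4).** "Each lower limb amputation, disarticulation, or auto-amputation should be reported separately".

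The safety lists in Protocol 2.2 and SAP 2.2.3 include all-cause mortality and the numbers of serious adverse events, hypoglycaemic events, genital infections and ketoacidotic events. Liver and kidney appear as "Changes in liver function parameters (AST, ALT, GGT" and "Changes in renal function parameters (creatinine, eGFR". Amputation is not listed. The SAP mentions AESIs only in its abbreviation list, and the 6.5 thresholds appear nowhere in it.

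SAP 5 gives methods for the primary and secondary endpoints only. SAP 6 states: "All continuous variables will be summarized using the following descriptive statistics: n (non-missing sample size), mean, standard deviation". Protocol 7.2 adds generic between-group tests.

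**The concern.** Each AESI is an event in one patient: a threshold crossed, or a procedure performed. A change in a laboratory value averaged over an arm does not measure that. A few severe cases barely move a mean, and a case with no week-52 sample does not enter it. The report could state that liver and renal values did not change while the arms differed in the injuries the protocol itself singled out. For amputation the plan gives no separate result at all.

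**Working it through.** **Step 1. Each AESI against the safety endpoints and the analysis text.**

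| AESI (Protocol 6.5) | Endpoint in Protocol 2.2 / SAP 2.2.3 | Event count by the 6.5 definition? |
|---|---|---|
| Hepatic injury | Changes in AST, ALT, GGT | No; no threshold and no bilirubin |
| Decreased renal function | Changes in creatinine, eGFR | No; no threshold |
| Metabolic acidosis / ketoacidosis / DKA | Number of ketoacidotic events | In part; non-keto metabolic acidosis is not counted |
| Lower-limb amputation | None of its own; within total serious adverse events | No; not identifiable there |

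So three of the four have no event-level endpoint.

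**Step 2. What the laboratory endpoints can show.** The visit schedule and Table 2 (Protocol 5.3 and 5.5.5) place blood tests at visit 1 and visit 2 (week 52 ± 4). Visit 3 is by telephone. A change score therefore needs a visit 2 sample. An injury that resolved before visit 2 is measured after recovery. A patient who died or withdrew before visit 2 has no scheduled value. SAP 5.2 plans imputation for the primary analyses only. The unscheduled creatinine samples required by Protocol 6.5.2 enter no stated analysis.

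**Step 3. How far a few injuries move a mean.** If m of n patients in an arm exactly double their creatinine, have average baseline values and are all sampled at week 52, then

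shift in the arm mean = (m / n) × mean baseline.

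The planned total of 402 gives n = 402 / 2 = 201 per arm:

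- m = 2: 2/201 = 1.0% of mean baseline
- m = 4: 4/201 = 2.0%
- m = 6: 6/201 = 3.0%

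With an assumed baseline of 1.2 mg/dL, four doublings shift the mean by 0.020 × 1.2 = 0.024 mg/dL. SAP 7 records early termination and a smaller sample but gives no figure. At an assumed 100 per arm, two doublings give the same shift: 2/100 × 1.2 = 0.024 mg/dL.

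For the liver, take an assumed rise in ALT from 25 to 175 U/L (5 times an assumed ULN of 35). Two cases in 201 shift the mean by 2/201 × 150 = 1.5 U/L, and four shift it by 3.0 U/L.

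A reader would pass over shifts of this size. The same cases listed as two or four defined injuries would be noticed.

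**Step 4. Which definitions can be counted from the data.** Total bilirubin is in neither the visit schedule nor Table 2. The first hepatic criterion needs bilirubin in the same sample, so it can be assessed only where bilirubin was measured outside the schedule. The 5-fold ALT/AST criterion, creatinine doubling and amputation do not depend on bilirubin.

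**The case against.** The strongest reply is that little is lost:

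- Ketoacidotic events are counted in both documents.
- An amputation is handled through an SAE report, and an injury that is fatal, life-threatening or leads to admission is serious by Protocol 6.6. Such cases enter the serious adverse event and mortality endpoints.
- Protocol 6.4 has clinically significant abnormal laboratory results recorded as adverse events, apart from creatine kinase and NT-proBNP.
- SAP 6 sets out every summary table by arm, with frequencies and percentages for categorical variables. Protocol 7.2 allows median and IQR for skewed variables and supplies generic t, Mann–Whitney and χ² tests.

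All of this stands, and it rules out a tempting stronger reading: that the AESIs are not analysed, or that the safety plan is blind to deaths and serious injuries. The documents do not support that. What remains is that none of these provisions identifies an AESI by type. A total count of serious adverse events does not show how many were amputations, the generic tests define no AESI event, and no adverse event table by type is planned.

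A reader might also infer that counting would turn a missed signal into a significant one. It need not. An assumed split of 6 v 1 among 201 per arm gives a two-sided Fisher p of 0.12, and the actual sample is smaller. The gain is that the events become visible and can be interpreted.

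**Conclusion.** The point holds as a reporting gap. Hepatic injury, decreased renal function and lower-limb amputation have no event-level safety endpoint, non-keto metabolic acidosis is uncounted, and SAP 5 states no method for any safety endpoint. This rests on a comparison of the two documents and on no assumed figure.

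The masking argument rests on two things: SAP 6 being applied to the listed changes, since the endpoint lines say only that changes are assessed and do not name the mean; and the simple illustration above, whose laboratory values and event numbers are assumed. Nothing here suggests that an imbalance occurred, or that the sample size or the primary analysis is affected. Nor can the first hepatic criterion be fully reconstructed from the scheduled samples.

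**What to change.** In SAP 2.2.3, list each Protocol 6.5 AESI as its own safety endpoint. In SAP 5, specify one table by arm giving, for each AESI:

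- the number and percentage of patients with at least one event, and the number of events;
- counts by the 6.5 definitions, from all scheduled and unscheduled samples and all AE/AESI reports, from randomisation to visit 3;
- a risk difference with 95% CI where the counts allow it.

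Add a patient listing, and keep the laboratory changes as supportive. Because 6.5.3 tabulates criteria for DKA only, say that the metabolic acidosis row counts reported events. State beside the table that total bilirubin was not a scheduled test, so the first hepatic criterion is counted only where bilirubin was measured, and that laboratory events between visits depend on unscheduled testing.

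The cost is SAP wording, one table and one listing. The downside is wide intervals, given few events and the reduced sample; for the rarest AESIs the counts and the listing will have to suffice.

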### **3 Study Methods**

#### **3.1 General Study Design and Plan**

This is a two arms randomized controlled multi-center, parallel-group, double-blinded trial. The control group is a placebo and the treated group is Ertugliflozin. The aim of the trial is to show superiority of Ertugliflozin over Placebo in HFrEF and HFmrEF patients with ICD±CRT therapy.

#### **3.2 Inclusion-Exclusion Criteria and General Study Population**

##### **3.2.1 Inclusion criteria**

- 1) HFrEF or HFmrEF and ICD±CRT therapy > 3 months
- 2) At least 10 documented non-sustained VTs within the last 12 months plus
  - nt-proBNP > 500pg/mL or
  - LV-EF < 35% or
  - hospitalization for heart failure within the last 12 months or
  - >100nsVTs within the last 12 months
- 3) Informed consent has to be given in written form.
- 4) eGFR > 30 ml/min/1.73m^2
- 5) Blood pressure before first drug dosing: RRsystolic > 100mmHg
- 6) Blood pressure before first drug dosing: RRdiastolic > 60mmHg
- 7) 18 – 80 years of age

##### **3.2.2 Exclusion criteria**

- 1) Any other form of diabetes mellitus than type 2 diabetes mellitus, history of diabetic ketoacidosis
- 2) Ongoing ventricular arrhythmia
- 3) Known allergy to SGLT-2 inhibitors
- 4) Hemodynamic instability as defined by intravenous administration of catecholamine, calcium-sensitizers or phosphodiesterase inhibitors

## **Ertugliflozin to Reduce Arrhythmic burden in ICD/CRT patientS (ERASe-Trial) – a phase III Study**

- 5) >1 episode of severe hypoglycemia within the last 6 months under treatment with insulin or sulfonylurea
- 6) planned catheter ablation for ventricular arrhythmia
- 7) planned explantation of ICD, or planned up/downgrade to/from CRT-D device.

### **3.3 Randomization**

After screening, all eligible patients for the trial will be randomised into one of the two arms of the study via Randomiser Software (Institute for Medical Informatics, Statistics and Documentation, Medical University of Graz, <http://www.randomizer.at>), which will be programmed with a randomisation schedule provided by an independent statistician. The randomisation will be stratified by site, by type 2 diabetes and by eGFR < 60 vs  $\geq$  60. Only the subject number will be recorded in the case report form (CRF). The investigator will maintain a personal subject identification list (subject numbers with the corresponding subject names) to enable records to be identified.

### **3.4 Study Assessments**

Data is collected according to the following schedule:

	Visit 1 (V1) Screening / Baseline	Visit 2 (V2) (Week 52 ± 4)	Visit 3 (V3) (4 weeks ± 1w after V2)
Informed Consent	X		
Inclusion/exclusion criteria	X		
Randomisation	X		
Demography, medical history	X		
Concomitant medication	X	X	
Vital signs	X	X	

**Ertugliflozin to Reduce Arrhythmic burden in ICD/CRT patientS (ERASe-Trial) – a phase III Study**

Height	X		
Weight	X	X	
Physical examination	X	X	
ECG	X		
Cardiac ultrasound	X	X	
Biobank sampling	X	X	
ICD interrogation	X	X	
nt-proBNP (local)	X	X	
6min walk test	X	X	
Blood sampling	X	X	
Liver function parameters (AST, ALT, GGT)	X	X	
Renal function parameters (creatinine, eGFR)	X	X	
Adverse Events		X	X
Dispense medication	X		
Drug accountability		X	
Safety assessment before discharge	X		

#### 4 Sample Size

Previous data showed that VT/VF episodes are decrease by two thirds within 6 months after initiation of sacubitril/valsartan in ICD±CRT patients (10). sVT/VF Episodes declined by 62.5% whereas nsVTs rate dropped by ~70%. Based on comparable effects on heart failure morbidity with either SGLT-2 inhibition or sacubitril/valsartan treatment we expect a profound reduction in sVT/VF in the treatment arm. Since data of the large SGLT2 outcome trials which did not focus on arrhythmias and their detection but only counted cases of sudden cardiac death have a signal of smaller effects we calculate with a decrease in the event rate of 30%. Moreover, the retrospective analysis by Martens et al provides a rather low event rate in their population. However, as pointed out in the Introduction other prospective randomized trials have considerably higher event rates. The sample size calculation is based

## Ertugliflozin to Reduce Arrhythmic burden in ICD/CRT patientS (ERASE-Trial) – a phase III Study

on the mathematical formula provided by Zhu and Lakkis for comparing event rates of two negative binomial distributions (11). We used the function `power.nb.test` of the package `MKmisc` in R that implements the results of the paper cited above. According to that formula, the parameters needed to calculate the sample size are: The expected yearly rate of VT/VF episodes in the control group ( $r_0$ ), The minimal clinical relevant effect (RR) defined here as the ratio of expected VT/VF episodes rates (RR = expected rate in treated/expected rate in control =  $r_1/r_0$ ), the average follow-up or treatment duration (duration), the negative binomial dispersion parameter ( $k$ ), the Type I error probability ( $\alpha$ ) and the power ( $1 - \beta$ ). To detect a 30% reduction in VT/VF episodes rate in the ertugliflozin group as compared to the placebo group (i.e. using RR = 0.70), with a power of 80% and an alpha-level of 0.05%, a sample size of 191 patients in each group is needed. In this sample size calculation, we assumed the dispersion parameter  $k$  to be 1.0, the expected yearly rate of VT/VF episodes in the control group (i.e.  $r_0$ ) to be 1.3 and an average follow-up of 11.4 months. To account for a dropout rate of about 5% in each group, we will need of 402 patients in total.

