Therefore, every improvement of heart failure should result in a reduction of ventricular arrhythmias. This has been shown extensively for beta-blockers(6), aldosterone-antagonists(7; 8), and ARNIs(9; 10). Large outcome studies with ACE inhibitors did only give limited insight in the type of arrhythmic events, their causes, and the effect of the treatments(11; 12), while studies analysing the rate of ventricular arrhythmias did show a significant reduction in these events(13).

Previous data showed that SGLT-2 inhibitor dapagliflozin (DAPA-HF) improved primary outcome in a HFrEF population comparable to sacubitril/valsartan in the PARADIGM trial(9) (both trials with a NNT of 21). Therefore, a comparable impact on heart failure morbidity and ventricular arrhythmias can be assumed for both drugs. Moreover, Martens et al. reported on a highly significant reduction of ventricular arrhythmias after initiation of sacubitril/valsartan in a retrospective analysis of 151 patients with an observation period of 6 months. The number of VT/VF episodes declined by more than two thirds(10).

Mortality in patients on ICD therapy is high despite optimal medical treatment. The study by Martens is a retrospective analysis of data of patients that were followed throughout the observation period of 364 days.

Therefore, severely ill patients and at least those who died within these 12 months were not analysed. Obviously, these patients tend to have the highest burden of ventricular arrhythmias. Therefore, event rate in the Martens study is underestimated.

More reliable data on event rates derive from prospective randomized trials such as the RAFT study. They report a rate of VTs of ~2 per year (11278 appropriate ICD detections in 5953.6 patient-years of follow-up) in a cohort of patients with severely reduced left ventricular ejection fraction (<30%).

Within another increased-risk population treated in the SHIELD trial 58% of the placebo-group experienced “all-cause shocks plus symptomatic tachyarrhythmias terminated by ATP”. The overall number of episodes was 1595 in 214 patients (average of ~7.5/patient and year).

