7.1 Sample size and power considerations

Previous data showed that VT/VF episodes are decrease by two thirds within 6 months after initiation of sacubitril/valsartan in ICD±CRT patients (10). sVT/VF Episodes declined by 62.5% whereas nsVTs rate dropped by ~70%. Based on comparable effects on heart failure morbidity with either SGLT-2 inhibition or sacubitril/valsartan treatment we expect a profound reduction in sVT/VF in the treatment arm. Since data of the large SGLT2 outcome trials which did not focus on arrhythmias and their detection but only counted cases of sudden cardiac death have a signal of smaller effects we calculate with a decrease in the event rate of 30%. Moreover, the retrospective analysis by Martens et al provides a rather low event rate in their population. However, as pointed out in the Introduction other prospective randomized trials have considerably higher event rates. The sample size calculation is based on the mathematical formula provided by Zhu and Lakkis for comparing event rates of two negative binomial distributions (19). We used the function power.nb.test of the package MKmisc in R that implements the results of the paper cited above. According to that formula, the parameters needed to calculate the sample size are: The expected yearly rate of VT/VF episodes in the control group (r_0), The minimal clinical relevant effect (RR) defined here as the ratio of expected VT/VF episodes rates (RR = expected rate in treated/expected rate in control = r_1/r_0), the average follow-up or treatment duration (duration), the negative binomial dispersion parameter (k), the Type I error probability (α) and the power ($1 - \beta$). To detect a 30% reduction in VT/VF episodes rate in the ertugliflozin group as compared to the placebo group (i.e. using RR = 0.70), with a power of 80% and an alpha-level of 0.05%, a sample size of 191 patients in each group is needed. In this sample size calculation, we assumed the dispersion parameter k to be 1.0, the expected yearly rate of VT/VF episodes in the control group (i.e. r_0) to be 1.0 and an average follow-up of 11.4 months. To account for a dropout rate of about 5% in each group, we will need of 402 patients in each arm.

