7.2 Data analysis

Intention-to-treat (ITT) analyses will be applied as the primary analysis. Analysis of the primary endpoint is comparison of the number of sVT/VF episodes between treatment groups from randomization to week 52. The primary endpoint will be analysed using analysis of covariance (ANCOVA), with treatment as a fixed factor, the baseline number of sVT/VF episodes as a covariate and with adjustment for history of T2D and eGFR and site of randomization.

Normally distributed variables will be presented as mean \pm standard deviation (SD) and skewed distributed variables as median and interquartile range [IQR]. Comparisons between treatment and placebo group will be performed by an unpaired two sample *t*-test, Mann–Whitney test, or χ^2 test as appropriate.

A two-tailed p-value ≤ 0.05 will be considered statistically significant. A detailed statistical analysis plan including pre-specified subgroup analyses will be finalized ahead of database lock.

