## **Ertugliflozin to Reduce Arrhythmic burden in ICD/CRT patientS (ERASe-Trial) – a phase III Study**

**RR =  $e^{\beta_1}$ .** The efficacy of the drug, compared to placebo, will then be investigated by testing the following null and alternative hypotheses:

$$H_0: \beta_1 = 0 \quad \text{vs.} \quad H_A: \beta_1 \neq 0$$

The function `glm.nb` from the MASS package in R will be used for this reason and for fitting the negative binomial regression model. The model will also adjust for the baseline number of sVT/VF. Sensitivity analysis will be carried out by using methods robust to outliers.

The analysis of secondary endpoints will be as follows: The number of incident nsVT, the number of appropriate ICD-treatment episodes, the total number of hospitalization due to heart failure will be analysed using a beta binomial model. The change in NTproBNP and the change in HbA1c levels from randomization to week 52 will be analysed using a multiple linear regression model. Hospitalization days from randomization to week 52 will be compared between the two groups using mean and SD. Cardiovascular mortality will be analysed by comparing proportions across the two groups.

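### 191 patients per group gives about 70% power (64% at the protocol's control rate), not the stated 80%, for the two-sided 5% test; the protocol and SAP also derive the same 191 from different control rates.

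*SAP*

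**What the plan says.** Protocol 7.1 and SAP section 4 carry nearly the same sample size text. Both cite the Zhu and Lakkis formula for two negative binomial rates, run with `power.nb.test` in R. Both assume a rate ratio of 0.70 and a dispersion k of 1.0, and both conclude: "with a power of 80% and an alpha-level of 0.05%, a sample size of 191 patients in each group is needed".

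The inputs and totals then differ:

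- **Control rate.** The SAP takes the yearly control rate "to be 1.3 and an average follow-up of 11.4 months". The protocol takes it "to be 1.0 and an average follow-up of 11.4 months".
- **Total after 5% dropout.** The SAP says "we will need of 402 patients in total". The protocol says "we will need of 402 patients in each arm", although its synopsis and section 3.1 give 402 for the whole trial.

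The test is two-sided in both documents. Protocol 7.2: "A two-tailed p-value ≤ 0.05 will be considered statistically significant". SAP section 5: "The efficacy of the drug, compared to placebo, will then be investigated by testing the following null and alternative hypotheses", followed by the alternative β1 ≠ 0. Neither document mentions a one-sided test.

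SAP section 7 says the plan was revised because the trial stopped early with fewer patients. Section 4 still carries the 80% power statement.

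**The concern.** Control rate, alpha, group size and power are tied together by one formula, so two control rates with everything else equal cannot both give 191. That alone means at least one document is wrong. It also raises the question of which inputs produced 191, and whether they match the test that will be run.

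The stake is how the primary result is read. A non-significant result in a trial described as having 80% power for a 30% reduction is easily taken as evidence against an effect of that size. If the planned power was materially lower, that reading is unsafe, and early termination makes it more so.

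**Working it through.** **Inputs** (Protocol 7.1, SAP section 4): RR = 0.70; k = 1.0; t = 11.4/12 = 0.95 year; equal groups; 80% power; r0 = 1.3 (SAP) or 1.0 (protocol); r1 = 0.70 × r0. Alpha is printed as 0.05%. I read it as 5%: taken literally, at r0 = 1.3 it would need 576 per group two-sided, and 191 would have about 16% power.

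**Formula.** Per group,

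n = [z_α·√V0 + z_β·√V1]² / (ln RR)², with V1 = (1/r0 + 1/r1)/t + 2k.

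The null variance V0 has three forms: pooled, 4/(t(r0 + r1)) + 2k; control rate, 2/(t·r0) + 2k; and V0 = V1. All three were tried. (ln 0.70)² = 0.1272.

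**Reproducing 191.** At r0 = 1.3, r1 = 0.91:

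- V1 = (1/1.3 + 1/0.91)/0.95 + 2 = 3.966, square root 1.992
- V0 (pooled) = 4/(0.95 × 2.21) + 2 = 3.905, square root 1.976
- One-sided 5%: n = (1.645 × 1.976 + 0.842 × 1.992)² / 0.1272 = 190.8, i.e. 191

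So 191 comes from r0 = 1.3 with a one-sided 5% test, equivalent to two-sided 10%.

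**The specified test.** Replacing 1.645 by 1.960 gives n = (1.960 × 1.976 + 0.842 × 1.992)² / 0.1272 = 242.1.

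| r0 | Test | n per group: pooled / control rate / V0 = V1 |
|---|---|---|
| 1.3 | one-sided 5% | 190.8 / 181.5 / 192.8 |
| 1.3 | two-sided 5% | 242.1 / 229.6 / 244.7 |
| 1.0 | one-sided 5% | 218.9 / 206.8 / 221.4 |
| 1.0 | two-sided 5% | 277.7 / 261.5 / 281.1 |

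The protocol's r0 = 1.0 does not give 191 in any row.

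**Power of 191 per group, two-sided 5%.** Power = Φ[(√n·|ln RR| − 1.960·√V0)/√V1]. With √191 × 0.3567 = 4.929:

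- r0 = 1.3: (4.929 − 1.960 × 1.976)/1.992 = 0.530, so 70.2% (69.7–72.7% across the three forms)
- r0 = 1.0: V1 = 4.556, V0 = 4.477; (4.929 − 1.960 × 2.116)/2.135 = 0.367, so 64.3% (63.7–67.3%)

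**Simulation.** Maximum likelihood negative binomial fits with a Wald test, 10,000 trials each, gave 69.8% at r0 = 1.3 and 63.5% at r0 = 1.0. At 1.3, one-sided 5% power was 79.7%. Two-sided type I error was 5.1–5.3%.

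**What 191 does support.** The rate ratio detectable with 80% power, two-sided 5%, is about 0.67 at r0 = 1.3 (0.666–0.676) and 0.65 at r0 = 1.0 (0.645–0.658). If the true rate ratio were 0.70, the expected 95% confidence interval would be about 0.53–0.93 or 0.52–0.95.

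**Dropout.** 2 × 191/0.95 = 402.1, so 402 is the total for both arms.

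**The case against.** The arithmetic is hard to dispute, but there are fair arguments that the shortfall is smaller or matters less.

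- **Patients who leave early still count.** The analysis is intention-to-treat with time at risk as offset, and 11.4 months is itself 95% of 12, so loss may have been allowed for twice. The documents do not explain the 11.4. With no loss at all, 201 per group gives 72.4% (r0 = 1.3) or 66.5% (r0 = 1.0). That narrows the gap slightly and does not close it.
- **The SAP model adjusts for baseline sVT/VF.** This is the strongest point. Adjustment can lower residual dispersion, and at r0 = 1.3 a residual k of about 0.6 would restore 80% (0.56–0.69 across the variance forms). At r0 = 1.0 it would have to fall to about 0.3 (0.27–0.43). Neither document gives a residual k or claims this gain, and the stated calculation uses k = 1.0.
- **Event rates may be higher.** The introduction cites "11278 appropriate ICD detections in 5953.6 patient-years of follow-up", i.e. 1.89 per year, and another trial with about 7.5. With k = 1, power at 191 would be 77% (77–79%) and about 90% respectively. These count different endpoints, dispersion could differ too, and neither calculation uses them. A two-sided 191 needs r0 of about 2.0–2.3.
- **The protocol's 1.0 may be a slip.** Probably so, since 191 fits only 1.3. In that case 70% is the relevant figure; 64% applies if 1.0 is kept.
- **The trial has ended early.** True, and no analysis or enrolment decision changes. But the SAP was revised for that reason and still prints 80%.

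**Conclusion.** The concern holds. The stated control rate, alpha, group size and power cannot all be true in either document. For the two-sided 5% test specified, 191 evaluable patients per group has about 70% power at r0 = 1.3 and 64% at r0 = 1.0, so a true 30% reduction would be missed in 30–36% of trials rather than 20%. Eighty per cent power would need about 243 per group (230–245) or 278 (262–282).

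This rests on k = 1.0, RR = 0.70 and 0.95 year as stated, on reading the printed alpha as 5%, and on an unadjusted negative binomial test. The 5% level comes from Protocol 7.2; SAP section 5 supplies the two-sided alternative but no numerical level. Any gain from baseline adjustment is unquantified. The choice of variance form moves power by about three percentage points and does not change the conclusion.

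**What to change.** In SAP section 4 and Protocol 7.1:

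1. State alpha as 5% two-sided.
2. Use one control rate in both documents. Of the two, only 1.3 is compatible with how 191 was obtained.
3. Replace the 80% claim. Suggested text: *With 191 evaluable patients per group, RR 0.70, k = 1.0, r0 = 1.3 and 11.4 months, a two-sided 5% test has about 70% power.* If r0 = 1.0 is kept, the figure is 64%. Alternatively, give the rate ratio detectable with 80% power (about 0.67 or 0.65).
4. In Protocol 7.1, correct 402 per arm to 402 in total.
5. In SAP section 4, label these figures as the original design, and report the number actually reached and the 95% confidence interval of the rate ratio.

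Because the trial has closed, a dated correction note to Protocol 7.1 would do; it leaves visible what was originally planned.

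The cost is one rerun of the sample size function and a few sentences. No extra patients are needed and the analysis does not change. The price is a less favourable power statement.
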